In addition, this proposal stems from a hospital-wide effort at Women & Infants Hospital (WIH) to reduce racial disparities among women of color in terms of frequency of severe maternal morbidity (SMM). SMM is a metric created by the Centers for Disease Control and Prevention that includes blood transfusion as well as adverse outcomes ranging from arrhythmia to eclampsia to intubation. SMM associated with hypertension is driven by asymptomatic postpartum hypertension. This is easily identified and managed prior to becoming SMM when patients adhere to recommended blood pressure checks after discharge. Excluding blood transfusion (which does not pertain to hypertension), the overall rate of SMM among women with hypertension during pregnancy who deliver at WIH is 6.6%. However, there is a significant difference along racial and ethnic lines: the rate of SMM in the setting of hypertension among black women is 6.8% compared to 4.5% among white women, and the rate of SMM in the setting of preeclampsia is 9.4% among Hispanic women compared to 4.9% among non-Hispanic women. The overall dual aim of the initiative is to reduce the disparity in rates of SMM among those with hypertension between black and white women and between Hispanic and non-Hispanic women by at least 33% by December 31, 2022. As part of WIH's equity initiative, automatic blood pressure cuffs (non Bluetooth enabled) will be provided to all women with hypertension at discharge from delivery hospitalization as part of

routine care. We plan to compare rates of SMM before versus after the hospital-wide implementation of SMS-based remote blood pressure monitoring. Thus, for this proposal, we will build the foundation for our long-term goal and for hospital-wide equity projects by exploring whether app-based remote blood pressure monitoring is required to decrease maternal morbidity compared to standard care with remote SMS blood pressure monitoring.

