2. STUDY DESIGN, METHODS, AND PROCEDURES

Study Design

2.1 Study Design: We will conduct a *pilot randomized control trial* of **120** women who deliver at Women and Infant's Hospital of Rhode Island (WIHRI) and plan to receive postpartum care at a WIHRI-affiliated clinic. We will use broad inclusion criteria and analyze data using the intention-to-treat principle to increase generalizability of the findings.

2.2 Eligibility criteria: Inclusion criteria: a) English- or Spanish-speaking b) maternal age ≥ 18 years old, c) smartphone ownership for remote blood pressure ascertainment, d) diagnosis of gestational hypertension, preeclampsia, or chronic hypertension, e) plan to receive postpartum care at a Women & Infants Hospital (WIH)-affiliated clinic. Exclusion criteria: a) fetal anomaly, b) prisoners, c) lack of smartphone, and d) inability to consent.

2.3 Screening, consent, and recruitment: Eligible women will be recruited at the Women and Infant's Hospital of Rhode Island (WIHRI) 's obstetrics units (obstetric triage, labor & delivery, antepartum care unit, and postpartum care unit) during their delivery hospitalization. Recruitment will be conducted by a research assistant or study principal investigator or co-investigator.

2.4 Randomization and blinding: Regardless of when their diagnosis of chronic hypertension, gestational hypertension, or preeclampsia with or without features occurs before or during delivery hospitalization, upon hospital discharge all patients will receive an automatic blood pressure cuff from WIHRI if their insurance does not cover this (or if they do not have one already); for patients whose insurance does cover automatic blood pressure cuffs, the provider will provide them with a prescription for this device at time of diagnosis. This is part of WIHRI's equity initiative related to hypertension: as stated previously, WIHRI has committed to provide non-Bluetooth enabled blood pressure cuffs to all eligible patients.

Those who consent to participate in the study, complete baseline study surveys, and receive a blood pressure cuff prior to discharge will be randomized 1:1 via a computer-generated randomization sequence to one of two protocols: *app based remote blood pressure monitoring* (intervention group) or and standard PNC with SMS-based monitoring (comparison group). The study staff will remain blinded to intervention, except for the research assistant who will be, by necessity, unblinded.

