Since starting recruitment, an additional challenge has developed: up to 10% of participants in the equity program (who may or may not be in the study) are discharged without blood pressure cuffs with the plan for a home visit to provide a BP cuff within 3-7 days after discharge. In addition, about 10% of patients who participated in the study did not complete their baseline study survey. To ensure we obtain a study population of 120 who follow the study protocol, we have developed an alternative approach by changing our inclusion criteria. Specifically, eligible people may be consented and randomized but only those who receive a BP cuff and complete their intake survey prior to discharge will be included in the trial's analytic population. We anticipate needed to randomize up to 160 patients in order to obtain our desired study population of 120 participants.

2.6 Study outcomes and Power:

Primary outcome: The primary outcomes will be adherence to recommended blood pressure check 3-10 days postpartum, as is recommended per standard of care. Our sample size of **120** pregnant women with gestational hypertension or preeclampsia will allow us to detect a 60% increase in adherence to recommended blood pressure check from the baseline rate of 50%, using a two-tailed alpha of 0.05. The 60% improvement (i.e. from 50% to 80% adherence) is conservative as it is less than has been reported in the medical literature.¹⁵⁻¹⁷ **Secondary outcomes:** Secondary outcomes will be surrogate markers of maternal morbidity.

Prespecified secondary outcomes include postpartum readmission for blood pressure management (e.g. hospital admission for blood pressure management within 30 days of discharge), adherence to evidence-based best-practices (e.g. medications, blood pressure ascertainment, postpartum blood pressure goal of $<140/90$), composite severe maternal morbidity (**Table 2**), and composite neonatal morbidity (Table 1). Our study will likely not be powered to detect differences in secondary outcomes due to the rarity of the individual patient outcomes but will provide us crucial pilot data for the subsequent study.

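### Cuff receipt before discharge is applied after randomisation to define who is analysed, and exclusions could differ by arm because only the app arm is given a study cuff

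*Combined protocol and SAP*

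**What the plan says.** All references are to the combined protocol and SAP.

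- **Criterion, section 2.4.** Women who consent, "complete baseline study surveys, and receive a blood pressure cuff prior to discharge will be randomized 1:1". On this wording the cuff comes before assignment.
- **Routine supply, section 2.4.** At discharge a patient gets an automatic cuff "from WIHRI if their insurance does not cover this (or if they do not have one already"). Where insurance does cover a cuff, "the provider will provide them with a prescription for this device at time of diagnosis".
- **Universal supply, sections 1 and 2.4.** The same paragraph of 2.4 ends by saying that "WIHRI has committed to provide non-Bluetooth enabled blood pressure cuffs to all eligible patients". The background says that non-Bluetooth cuffs "will be provided to all women with hypertension at discharge from delivery hospitalization".
- **Study cuff, section 2.4.** Women assigned to the app arm are given a Bluetooth cuff. No insurance or ownership condition is attached, and the time of hand-over is not stated.
- **Changed use, section 2.5 (potential challenges and alternative approaches).** Up to 10% of equity-programme participants leave without a cuff, and about 10% of study participants did not complete the baseline survey. Women may therefore be randomised first, and "only those who receive a BP cuff and complete their intake survey prior to discharge" enter the analytic population. Up to 160 are to be randomised to obtain 120.
- **Eligibility and analysis.** Section 2.2 lists no cuff requirement. Sections 2.1 and 2.7 promise an intention-to-treat analysis.

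**The concern.** A cuff rule checked before assignment can at most narrow the population; the randomised comparison stays fair. Once section 2.5 lets the rule be checked after assignment, it decides which randomised women are counted. It then matters whether the two arms have the same chance of passing.

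They may not. The study itself hands a cuff to one arm. The other arm depends on a routine supply rule that turns on insurance cover and perhaps on ownership. Women who leave hospital without a cuff may well differ from the rest in how likely they are to have a blood pressure check 3 to 10 days postpartum, which section 2.6 makes the primary outcome. Removing them from one arm and keeping their counterparts in the other would bias the comparison. In a trial with a health-equity aim, an exclusion that may track insurance is especially awkward.

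**Working it through.** **1. The plan's own figures.** With the two stated losses of 10%, 120 analysed women need 120 / (0.90 × 0.90) = 148.1, so 149 randomised if the losses are independent, or 120 / 0.80 = 150 if they add. The plan's 160 allows a total loss of 25% (160 × 0.75 = 120), so it covers both. Sixty per arm gives 94.1% power for 50% against 80% at two-sided 0.05 (normal approximation, pooled variance; 91.3% with Fisher's exact test). The plan states no power. Sample size is not the problem here.

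**2. What the criterion can mean once it is applied after assignment.**

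| Reading | App arm | Comparison arm | Consequence |
|---|---|---|---|
| A. Study cuff counts and is given before discharge | Criterion met by design | Met only through routine supply | Exclusions differ by arm |
| B. Study cuff does not count | Met only through routine supply | Same | No built-in difference, but an app-arm woman holding a study cuff can be excluded |
| C. Study cuff counts but arrives after discharge | Met only through routine supply | Same | No built-in difference |

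The text does not choose between these. All three remove randomised women from the analysis, which conflicts with 2.1 and 2.7. Reading A also makes the removal depend on arm.

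**3. Numbers under reading A.** Inputs: 160 randomised 1:1, so 80 per arm; 10% without a survey in both arms; 10% without a cuff in the comparison arm only. The 10% for cuffs is the plan's upper figure and describes programme participants, who may or may not be in the study. Losses are taken as independent.

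- App arm: 80 × 0.90 = 72.0 analysed.
- Comparison arm: 80 × 0.90 × 0.90 = 64.8 analysed.
- Difference: 7.2 women, all removed on the cuff criterion from one arm.

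Under B or C each arm keeps 64.8 on average.

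**4. How far the comparison-arm rate could move.** Let the rate among all comparison women be 50% (the plan's baseline), let 10% be excluded, and let *a* be adherence among the excluded. The documents do not give *a*, so the full range is shown.

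Rate among those kept = (0.50 − 0.10 × *a*) / 0.90

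| *a* | Rate among those kept | Difference from an app-arm rate of 80% |
|---|---|---|
| 0 | 0.500 / 0.90 = 55.6% | 24.4 points |
| 0.25 | 0.475 / 0.90 = 52.8% | 27.2 points |
| 0.50 | 0.450 / 0.90 = 50.0% | 30.0 points |
| 1 | 0.400 / 0.90 = 44.4% | 35.6 points |

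The shift is at most 5.6 points in either direction, against a planned difference of 30. If the app had no effect, the same shift would appear as a spurious difference of up to 5.6 points. The bound scales with the share excluded; 10% is the only share the plan gives.

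**The case against.** The strongest reply is that the wording is loose but staff would apply it sensibly. The cuff failure that section 2.5 describes is a woman who leaves with no cuff and awaits a home visit to be given one. That suggests the working test is possession at discharge. Two statements promise a cuff to everyone. On this view the word *receive* needs at most a clarifying note, and the arm difference rests on two things the plan does not say: that the study cuff counts, and that it is handed over before discharge.

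Much of this stands. In particular, a reader might infer from section 2.4 that entry to the trial depends on insurance and cuff ownership, with owners and prescription-only women shut out. The documents do not support that:

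- It needs the strictest reading of *receive*. Nothing says that an owned cuff or a filled prescription fails, and a prescription issued at diagnosis may be filled before discharge.
- The supply clause is joined by *or*. Read literally, it gives a hospital cuff to an owner without cover and to a covered woman who has none, so it does not clearly deny owners a cuff.
- After the change in 2.5 the criterion governs inclusion in the analysis rather than entry.

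Nor can one infer that owners and prescription-only women come on top of the stated 10%. A woman leaving with an unfilled prescription and no cuff may already be in that figure, and the documents give no share for either group.

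What the reply does not meet is the timing. However sensibly *receive* is read, section 2.5 applies it to women already randomised, and nothing prevents reading A.

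**Conclusion.** The point holds as a post-randomisation exclusion that can differ by arm, resting on a criterion the plan does not define. The conflict with intention-to-treat is there on any reading. The arm difference is conditional on the study cuff counting and being given before discharge. The dependence on insurance is likewise a possibility left open by the supply rule, not an established effect.

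Under those conditions, and with the plan's upper figure of 10%, the imbalance is about 7 women of 80 and the possible shift in the comparison-arm rate is up to 5.6 points. The direction cannot be told from the documents. That would not by itself create or erase a 30-point effect, but it is avoidable bias in a pilot whose estimates are meant to inform the next trial. The change is worth making because it is cheap and removes the problem entirely.

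**What to change.** 1. Reconcile the supply statements in section 1 and section 2.4, and the order of events in 2.4 and 2.5.
2. State the criterion in section 2.2: an automatic cuff in hand from any source (owned, filled prescription or hospital-supplied), not counting the study Bluetooth cuff.
3. Check it, with baseline survey completion, before assignment and on the same terms for all women. This restores the order already written in 2.4.
4. Analyse every randomised woman in her assigned arm, including those already randomised without meeting the criterion. The population restricted to women who met it can be reported as a sensitivity analysis.
5. Add a REDCap field for cuff source and report it by arm; insurance type is already collected.

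**Cost.** A few sentences in the protocol and one data field. Assignment has to wait until the cuff is in hand, which leaves less time before discharge for app set-up. Owned cuffs vary in model. Women with an unfilled prescription and no cuff are still not enrolled, so the change protects the comparison without fully widening access; recording the reason for non-enrolment would show how many are affected.

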They will receive the following per their randomization group:

Standard care (comparison group)

All women will receive education and counseling from their physician providers on evidence-based best-practices and red-flags for pregnancy's complicated by chronic hypertension, preeclampsia, or gestational hypertension. They will participate in WIHRI's ongoing equity initiative using automatic blood pressure cuffs in a remote hypertension monitoring program supported by a nurse practitioner and community health worker.

App-based remote blood pressure monitoring (intervention group)

Women in this group will receive a Bluetooth-enabled automatic blood pressure cuff that sends messages through an affiliated smartphone application to providers upon recording each measurement. This affiliated smartphone application will also contain education on hypertension management. Upon receipt of the blood pressure cuff, participants will be instructed to set up the program/app such that the research assistant (RA) will receive all recorded blood pressure managements. All patients will receive instructions on how to obtain blood pressure and will be instructed to call their on-call provider if the blood pressure is $>160/110$ mmHg. The RA will review each patient's blood pressure log daily to ensure blood pressures remain mild-range (i.e. 140-159/90-109 mmHg) or less.

2.5 Study procedures: Perinatal data will be collected and directly entered by the research assistant or principal investigators into REDCap, a secure database hosted by WIHRI. Data will be collected on a rolling basis to ensure timely collection and monitoring for unseen adverse events.

Potential challenges and alternative approaches: Obtaining our target sample size may be challenging due to the incidence of hypertension diseases of pregnancy in the literature. However, we anticipate having a sufficient population from which to recruit for this pilot study given the 18 month study period and the relatively small sample study. However, should our target sample size be lower than expected, we may expand recruitment into private practice groups who have separate admitting privileges.

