We will also explore patient preferences as to treatment group via the Agency for Healthcare Research and Quality Consumer Assessment of Healthcare Providers and Systems (AHRQ CAHPS) survey and compared between both intervention groups and standard prenatal care.²⁵ Per AHRQ guidelines, 100 CAHPS surveys must be completed in a pilot study to determine a difference in patient experience between care models.²⁵ Our study population of **60 women** per group (120 women total) is anticipated to generate ~100 completed surveys per group (200 total), based on an anticipated response rate of 80% and each participant completing two surveys. Upon enrollment, participants will choose whether they desire to complete the AHRQ CAHPS surveys in paper, online through email, or via a text-message platform; regardless of route, surveys will be collected at randomization and at ~30-45 days postpartum.

On the second survey, participants will also complete a validated scale, the Decision Regret Scale.²⁶ Of note, both the AHRQ CAHPS study and the Decision Regret Study are already validated in Spanish.

2.6 Data Management, Sources of Materials, Records/Data to be reviewed: Antepartum, maternal/neonatal, pregnancy, and perinatal data will be collected and directly entered by the research assistant or principal investigator into REDCap, a secure database hosted by WIHRI. All primary and secondary outcomes will be entered into REDCap by the RA or study team. Thus, the data to be reviewed will only be collected by key study personnel. In addition, pregnancy characteristics (maternal weight, disease comorbidities, etc.) and demographic information (reported race/ethnicity, insurance type, zip code) will be collected post-delivery and entered into REDCap. Prior to data analysis, all patient identifiable information will be stripped to ensure patient confidentiality. Our REDCap database will be encrypted by multiple levels of password protection (accessing computer, network, and logging into database) that will only be accessible by key research personnel. Anti-virus software is installed and up to date and the operating system is up to date with all Windows and Apple updates.

Material/Specimen Management: No specimens will be stored outside of standard care (such as umbilical cord gases processed by laboratory per usual clinical protocol).

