Provisions to monitor the data to ensure the safety of subjects: Our study does not involve greater than minimal risk. However, we will monitor for unanticipated adverse outcomes. As a part of this, key study personnel (Drs. [name], [name]) will monitor for adverse outcomes on a weekly basis. Should any unanticipated outcomes be found, this will be reported back to the IRB. Beyond the weekly monitoring of patients/data, this will also be performed globally on a quarterly basis.

Withdrawal of subjects: Patients will not be withdrawn from the study.

2.7 Data analysis: Analysis will follow the intention-to-treat principle. Continuous variables will be compared using the Student's *t*-test or Mann Whitney *U* test, as appropriate. Categorical variables will be compared using the χ^2 or Fisher's exact test, as appropriate. We will calculate crude and unadjusted risk ratios and differences. We will use multivariable logistic regression to adjust for potential confounders. Qualitative data obtained from CAHPS survey will also be analyzed using Nvivo, a computer-assisted qualitative data analysis software provided by Brown University. This software promotes inquiry beyond coding, sorting and retrieval of data. It is designed to integrate coding with qualitative linking, shaping, and modeling that may inform health equitable care. [name] and [name] have used Nvivo software. In addition, [name] has utilized this procedure to capture qualitative data previously to successfully design, implement, and launch a new model of health care for vulnerable patients transitioning from the hospital to sub-acute care facilities.²⁷

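### Minor safety wording error: participants are told to call above 160/110 mmHg, but the acceptable range ends at 159/109, so a reading of exactly 160 or 110 can prompt no call

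*Combined protocol and SAP*

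**What the plan says.** The relevant text is in section 2.4 of the combined protocol and SAP, under the sub-heading for the app-based intervention group. Two consecutive sentences each set a limit.

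- **Participant's limit.** Participants are "instructed to call their on-call provider if the blood pressure is" strictly greater than 160/110 mmHg. The sentence stands under the intervention heading but is addressed to all patients.
- **Research assistant's limit.** The research assistant checks each log daily to "ensure blood pressures remain mild-range (i.e. 140-159/90-109 mmHg) or less".

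The same paragraph describes a second route for the reading: the cuff "sends messages through an affiliated smartphone application to providers upon recording each measurement", and the app is set up so that the research assistant receives every recorded value. The paragraph does not say what the research assistant does on finding a value out of range.

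**The concern.** The two limits should meet and do not. The acceptable range stops at 159/109 and the call rule starts at 161 systolic or 111 diastolic, so the values 160 and 110 belong to neither. A woman who sees 160/100 on her cuff has a pressure that the protocol does not count as mild, yet read literally her instruction does not ask her to call.

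This is the only numeric call threshold for participants in the documents, and the only response to a high reading that the protocol spells out. Section 1 says that severe morbidity associated with hypertension is driven by asymptomatic postpartum hypertension. A woman without symptoms has little but the displayed number to act on, so the number in her instruction should be right.

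The slash adds a second uncertainty. The sentence does not say whether one component above its limit is enough or whether both are needed.

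**Working it through.** The plan states no figure to reproduce here. The check has three parts: whether the gap exists, whether other text closes it, and roughly how wide it is.

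**1. The gap, from the protocol's own limits**

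Write S for systolic and D for diastolic, in whole mmHg.

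- Above mild range: S > 159 or D > 109.
- Call rule, either component: S > 160 or D > 110.
- Call rule, both components: S > 160 and D > 110.

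| Reading | Above mild range? | Call, if either | Call, if both |
|---|---|---|---|
| 160/100 | yes | no | no |
| 150/110 | yes | no | no |
| 160/110 | yes | no | no |
| 160/115 | yes | yes (diastolic) | no |
| 190/100 | yes | yes (systolic) | no |

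Listing all whole-number pairs with S from 80 to 220, D from 40 to 140 and D < S confirms this.

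- Under the either-component reading, the uncovered pairs are exactly S = 160 with D from 40 to 110 (71 pairs) and D = 110 with S from 111 to 160 (50 pairs). They share one pair, so 71 + 50 - 1 = 120.
- Under the both-components reading, 5,415 pairs are uncovered, and these include all 120.
- With the rule changed to S >= 160 or D >= 110, none are uncovered.

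These counts show the shape of the gap, not how often women would fall in it.

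**2. Other text that might close it**

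- Comparison-group text in section 2.4: "All women will receive education and counseling from their physician providers on evidence-based best-practices and red-flags". No number is attached.
- Section 2.6 lists adherence items: "medications, blood pressure ascertainment, postpartum blood pressure goal of" below 140/90. Section 1 gives the same figure. It is an outcome goal, not a call rule.
- The safety-monitoring paragraph: study personnel "will monitor for adverse outcomes on a weekly basis". No pressure limit is set.

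None of these supplies a participant threshold.

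**3. Approximate frequency, on assumed inputs**

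The documents give no blood pressure distribution, so every input here is an assumption: systolic mean 130, 135 or 140 with SD 12, 15 or 18; diastolic mean 80, 85 or 90 with SD 8, 10 or 12; correlation 0.5, 0.65 or 0.8. That makes 3 x 3 x 3 x 3 x 3 = 243 combinations. Readings are bivariate normal, rounded to whole numbers (limits taken at .5), and the rule is read as either component.

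- Gap share = P(S <= 160 and D <= 110) - P(S <= 159 and D <= 109).
- Share above mild range = 1 - P(S <= 159 and D <= 109).

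| Case | Assumed S mean/SD, D mean/SD, correlation | Gap share of all readings |
|---|---|---|
| Lowest | 130/12, 80/8, 0.8 | 0.00147 |
| Middle | 135/15, 85/10, 0.65 | 0.00734 |
| Highest | 140/18, 90/12, 0.5 | 0.01595 |

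That is about 1 to 16 per 1,000 readings, or 7 per 1,000 in the middle case. In the middle case the share above mild range is 0.0542, so the gap holds 0.00734 / 0.0542 = 13.6% of those readings. Across all combinations this proportion runs from 8.6% to 25.0%.

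The protocol gives neither a reading frequency nor a monitoring length, so these shares cannot be turned into a count of readings per arm.

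**The case against.** The strongest reply is that the two sentences set limits for two different actors. A surveillance limit slightly below a self-call limit is an ordinary two-tier arrangement, nothing says the two must coincide, and the documents never define a severe range as starting at 160/110. Part of this stands: a mismatch between tiers is not in itself an error. It does not rescue the text, because the protocol gives no purpose for a tier 1 mmHg wide and states no research assistant action for readings in it. If the intended rule was at or above 160/110, the sentence is wrong. If the strict rule was intended, it leaves an unexplained hole beside the next sentence.

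The second reply is that the reading is seen anyway, through the app and the daily review. This stands and sets the severity. What is lost is the woman's own prompt to call when she sees the number. A reader might infer that dangerous readings go unnoticed in the intervention arm; the documents do not support that, since each measurement is transmitted and the log is checked every day.

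The third reply is that the participant materials are not among the documents and may already carry the right wording. That is fair. The criticism is of the protocol sentence, not of what women were in fact told.

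The fourth concerns scope. A reader might assume that a correction touches only the intervention arm. Because the sentence is addressed to all patients, that is not secure.

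**Conclusion.** The point holds as a minor wrong-as-written safety threshold. From the protocol's own numbers, a reading of exactly 160 systolic or 110 diastolic, with the other component not above its limit, is above mild range and prompts no participant call. This is true under either reading of the slash and depends on no assumption. The both-components reading makes the gap much larger, so the and/or ambiguity matters at least as much as the inequality sign.

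The frequency is not known. The figure of 1 to 16 per 1,000 readings rests wholly on assumed distributions and the either-component reading, and shows only that the gap is small and not empty.

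A reader might infer that the trial's results are at risk. They are not: the threshold does not enter the sample size, the power or the primary analysis. Severity is the lowest level.

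**What to change.** Change the instruction in section 2.4 to: call the on-call provider if systolic is >=160 or diastolic is >=110 mmHg. This meets the research assistant's 159/109 limit exactly and settles the either/both question.

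Apply it to every participant who receives the instruction, and state whether that includes the comparison arm. Make the matching change in the participant instructions in English and Spanish, since section 2.2 admits speakers of both. Section 2.5 shows that recruitment has begun, so women already enrolled and still being monitored should be told as well.

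The cost is one protocol sentence, the matching participant wording in two languages, a message to current participants, and a few more boundary calls. The number of calls cannot be derived from the documents. On the assumptions above it is about 1 to 16 per 1,000 readings if women already read the rule as either component, and more if some now read it as both.
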